### 10.1.10 Day 43 Visit (C2D15)

The MOR03087 vial(s) have to be obtained from the freezer 3 days to 16 hours before planned start of study drug administration. The vials have to be thawed and stored at 2-8°C until preparation for administration.

The following will be obtained, performed, or assessed prior to study drug administration:

- Toxicity/AE assessment since the last visit
- Concomitant medication
- Karnofsky performance status
- Blood sample for "emergency laboratory" for immediate evaluation before study drug administration (only to be taken if hematology/serum chemistry is not available prior to study drug administration), hematology, serum chemistry, endocrinology, anti-MOR03087 antibodies, serum M-protein, serum FLCs, and predose pharmacokinetics (MOR03087)
- Sample from 24-hour urine for urine M-protein
- Physical examination (including basic neurological examination of general motor and sensory systems, mental status, cranial nerves, and coordination)
- Body weight
- Quality of life questionnaires (QLQ-MY20 and QLQ-C30)
- Vital signs (blood pressure, pulse rate, respiratory rate, and body temperature)
- Premedication (at the investigator's discretion if no infusion reaction during Cycle 1)

For subjects receiving weekly treatment, the additional following will be obtained, performed, or assessed prior to study drug administration:

- Blood sample for predose pharmacokinetics (LEN / POM)
- Clinical review of signs/symptoms for possible VTEs in subjects treated with POM or LEN. Subjects who develop symptomatic deep vein thrombosis will be assessed and diagnosed objectively by Doppler ultrasonography or a comparable method per institution's standard of care. See Appendix 18.9 for deep vein thrombosis and pulmonary embolism diagnostic algorithms
- Prophylactic treatment of thromboembolism for subjects enrolled into the LEN or POM cohorts
- For subjects treated with LEN, 12-lead ECG may be performed at the investigator's discretion

Study drug administration:

- MOR03087 Study drug administration
- DEX, POM, LEN administration according to cohort assignment; POM and LEN will be administered daily on Days 1-21 of each 28-day cycle; time point for oral application of POM or LEN at start of MOR03087 infusion (+/- 5min). DEX should be given up to 3 hours prior to MOR03087 infusion start.

The following will be obtained, performed, or assessed after start of study drug administration:

- Vital signs (blood pressure, pulse rate, respiratory rate, and body temperature) at 15 minutes, 30 minutes, and 1 hour after start of infusion; end of infusion; and 2 and 4 hours after end of infusion
- Blood sample for MOR03087 pharmacokinetics (after completion of infusion)
- Ongoing toxicity/AE assessment during the visit

For subjects receiving weekly treatment, the additional following will be obtained, performed, or assessed after study drug administration:

• According to cohort assignment blood samples for POM or LEN pharmacokinetics (after completion of infusion)

### 10.1.11 Day 50 Visit (C2D22)

On Day 50, the following will be obtained, performed, or assessed:

- Toxicity/AE assessment since last visit
- Concomitant medications
- Blood sample for hematology, serum chemistry, and pharmacokinetics (MOR03087)
- Physical examination (including basic neurological examination of general motor and sensory systems, mental status, cranial nerves, and coordination)
- Vital signs (blood pressure, pulse rate, respiratory rate, and body temperature)

For subjects receiving weekly treatment, the additional following will be obtained, performed, or assessed prior to study drug administration:

- Blood sample for "emergency laboratory" for immediate evaluation before study drug administration (only to be taken if hematology/serum chemistry is not available prior to study drug administration)
- Body weight
- 12-Lead ECG (for subjects treated with LEN this assessment is at the investigator's discretion)
- Clinical review of signs/symptoms for possible VTEs in subjects treated with POM or LEN. Subjects who develop symptomatic deep vein thrombosis will be assessed and diagnosed objectively by Doppler ultrasonography or a comparable method per institution's standard of care. See Appendix 18.9 for deep vein thrombosis and pulmonary embolism diagnostic algorithms
- Prophylactic treatment of thromboembolism for subjects enrolled into the LEN or POM cohorts
- Premedication (at the investigator's discretion if no infusion reaction during Cycle 1)

For subjects receiving weekly treatment, study drug administration:

- MOR03087 Study drug administration
- DEX administration according to cohort assignment. DEX should be given up to 3 hours prior to MOR03087 infusion start.

For all cohorts the following will be obtained, performed, or assessed after start of study drug administration:

- Vital signs (blood pressure, pulse rate, respiratory rate, and body temperature) at 15 minutes, 30 minutes, and 1 hour after start of infusion; end of infusion; and 2 and 4 hours after end of infusion
- Blood sample for MOR03087 pharmacokinetics (after completion of infusion)
- Ongoing toxicity/AE assessment during the visit

## 10.1.12 Follow-Up Visits

## Follow-Up Visit 1:

After treatment discontinuation without disease progression a follow-up visit will occur 4 weeks  $(\pm 2 \text{ days})$  after the last dose of study drug.

At this visit, the following will be obtained, performed, or assessed:

- Toxicity/AE assessment since the last visit
- Concomitant medications
- Karnofsky performance status
- Blood sample for hematology, serum chemistry, coagulation, βHCG pregnancy test for women of childbearing potential, endocrinology, anti-MOR03087 antibodies, serum M-protein, serum FLCs, pharmacokinetics (MOR03087), and B, T, and NK cells
- Sample from 24-hour urine for urine M-protein
- Response assessment. Note: all responses require two consecutive assessments, and should ideally be confirmed.
- Physical examination (including basic neurological examination of general motor and sensory systems, mental status, cranial nerves, and coordination)
- Body weight
- Quality of life questionnaires (QLQ-MY20 and QLQ-C30)
- 12-Lead ECG, if clinically indicated at the discretion of the investigator
- Vital signs (blood pressure, pulse rate, respiratory rate, and body temperature)

For subjects receiving POM or LEN, the additional following will be obtained, performed, or assessed:

• Clinical review of signs/symptoms for possible VTEs in subjects treated with POM or LEN. Subjects who develop symptomatic deep vein thrombosis will be assessed and diagnosed objectively by Doppler ultrasonography or a comparable method per institution's standard of care. See Appendix 18.9 for deep vein thrombosis and pulmonary embolism diagnostic algorithms

For women of childbearing potential with irregular cycles in study cohorts that include LEN or POM, a pregnancy test (serum or urine) is to be performed 14 days after treatment discontinuation.

#### Follow-Up Visit 2 and Subsequent Follow-Up Visits:

Four weeks ( $\pm 2$  days) after Follow-up Visit 1, a second follow-up visit will occur. If there is still a response to therapy at this visit, then a follow-up visit will be repeated every fourth week ( $\pm 2$  days) until there is a disease progression (but no longer than 3 years), death, or the subject starts a new anti-myeloma therapy. Follow-up visits may be delayed for a maximum of 2 weeks after the normal visit window due to other reasons (e.g., logistical).

At each of these visits, the following will be obtained, performed, or assessed:

- Toxicity/AE assessment since the last visit
- Concomitant medication
- Karnofsky performance status
- Blood sample for hematology, serum chemistry, βHCG pregnancy test for women of childbearing potential, anti-MOR03087 antibodies (at Follow-up Visit 2 only), B, T, and NK cells, serum M-protein, and serum FLCs
- Sample from 24-hour urine for urine M-protein
- Response assessment, to be continued until disease progression or death or subsequent anti MM therapy start whatever occurs first. Note: all responses require two consecutive assessments, and should ideally be confirmed at the next follow-up visit.
- Physical examination (including basic neurological examination of general motor and sensory systems, mental status, cranial nerves, and coordination)
- Body weight
- Quality of life questionnaires (QLQ-MY20 and QLQ-C30)
- 12-Lead ECG, if clinically indicated at the discretion of the investigator
- Vital signs (blood pressure, pulse rate, respiratory rate, and body temperature)
- Clinical review of signs/symptoms for possible VTEs in subjects treated with POM or LEN. Subjects who develop symptomatic deep vein thrombosis will be assessed and diagnosed objectively by Doppler ultrasonography or a comparable method per institution's standard of care. See Appendix 18.9 for deep vein thrombosis and pulmonary embolism diagnostic algorithms

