Following completion of Parts D and E (dose escalation of MOR03087 in combination with POM+DEX and LEN+DEX), the MTD and/or recommended dose in each part will be confirmed in a minimum of 6 subjects.

All cohorts:

After the first administration of study drug, the subjects will remain at the site until the end of Day 2 for safety monitoring. The subjects will not stay overnight at the site for subsequent administrations.

Based on the individual risk/benefit ratio, subjects who have an ongoing response of at least stable disease (SD) may continue treatment with the assigned study regimen until disease progression or until a maximum of 3 years after first treatment. In case subjects present with progressive disease or with no better status than SD after four treatment cycles starting with Cycle 1 Day 1, the investigator may add a low weekly dose of DEX to the regimen at his/her discretion, provided DEX is not already part of the treatment regimen.

At least 3 subjects meeting all inclusion and none of the exclusion criteria, as determined at the screening visit (see Sections 8.1 and 8.2) will be enrolled into each cohort.

Enrolment into a cohort at the next higher dose level will be based on the data generated from the previous dose level and guided by clinical review until

- the maximum planned dose has been reached, or
- the review of the safety data indicates a need to either expand the current dose level cohort to include 6 subjects or stop the dose escalation or the study, or
- the review of Part B dose level 6b and Part C dose level 6c, including available safety information from Part A dose level 8, indicates that only some of the planned weekly MOR03087 monotherapy dose escalation cohorts should be tested.

The DMC safety review will take place after the third subject enrolled into a cohort has undergone minimum safety evaluations (as defined for the "DLT Evaluable Population" in Section 15.1). The safety assessment will take into account AEs reported from Day 1 after the start of the first infusion through Day 29 before the start of the second cycle. The next cohort will only be started after the positive outcome of the safety assessment.

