Cohort expansion up to 6 subjects will be allowed if a dose limiting toxicity (DLT) (as defined in Section 8.5) is observed in 1 of 3 subjects. If 2 or 3 subjects experience a DLT in cohorts 6b or 6c, the study sponsor may decide to test a lower dose. If 2 or 3 subjects of the 3 subjects in any of the other cohorts experience DLT, then the previous cohort should be expanded to 6 subjects.

A pharmacokinetic interim analysis may be performed at any time during dose escalation if unexpected MOR03087 serum concentration results are observed. The rationale for performing the pharmacokinetic interim analysis is to verify whether the derived pharmacokinetic parameters from this interim analysis (e.g., C_{max} , AUC, terminal elimination half-life, etc.) are still within the expected range. If there are major deviations from the expected values, it may be considered necessary to investigate a further dosing regimen or to expand the dose escalation including further cohorts via a substantial amendment to the protocol.

After study drug discontinuation due to reason other than disease progression, all subjects will return for a follow-up visit 1 and follow-up visit 2. Further follow-up visits will be conducted at 4-week intervals until the subject is progressive, begins subsequent anti-myeloma therapy, or dies.

All subjects will be followed up for a maximum of 3 years after first administration of study drug.

Study visits will be conducted according to the Schedules of Assessments provided in Table 1 (for subjects receiving bi-weekly MOR03087 treatment) and Table 2 (for subjects receiving weekly/bi-weekly MOR03087 treatment).

]	Freatme	nt (Tx) C	Cycle 1 (I	Days 1-28	8)	Тх	Cycle 2	(Days 29	-56)	Tx Cycles 3+	Follow-up	Follow-up Visit 2	EOS Visit ²
Evaluation or Procedure	Screening (≤ 4 weeks before Day 1)	D1	D2	D4	D8 ± 1 day	D15 ±1 day	D22 ±1 day	D29 C2D1 ±1 day	D36 C2D8 ± 1 day	D43 C2D15 ± 1 day	D50 C2D22 ± 1 day	Visit: repeated bi- weekly (± 2 days)	Visit 1 (4 weeks ± 2 days after last dose)	(4 weeks ± 2 days after Follow-up Visit 1) ¹	
Informed consent	X														
Medical history ³	X														
Demography	X														
Inclusion/exclusion criteria	X	X ⁴													
Karnofsky performance status	X	X ⁴								X4		X^5	Х	Х	Х
Premedication		X ⁶		X ⁶		X ⁶		X ⁶		X ⁶		X ⁶			
Study drug administration (2-hour infusion)		Х		X		Х		X		X		Х			
Laboratory															
"Emergency laboratory"7		X ⁸		X8		X ⁸		X8		X8		X			

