¹ A follow-up visit will be repeated every fourth week (± 2 days) until progressive disease, or receipt of new anti-myeloma treatment, or until death, but no longer than 3 years from the first study drug administration. Follow-up visits may be delayed for a maximum of 2 weeks after the normal visit window due to other reasons (e.g., logistical).

² The EOS visit will occur after at least 28 days after last study drug administration but should be performed before any new MM therapy starts, whichever occurs first. Subjects who complete Cycle 2 but do not receive additional cycles (Cycle 3+) have to perform Follow-up visit 1 and Follow-up visit 2 before EOS visit.

³ Including disease staging based on Durie-Salmon and International Staging System (ISS) criteria and documentation of immunoglobulin type.

⁴Before study drug administration.

⁵ Each cycle, starting with Cycle 3+: pre-dose at Day 1 (CxD1)

⁶ During Cycle 1, all subjects should be given premedication including an antipyretic (e.g., paracetamol) and a histamine H1 receptor blocker according to the local standard of care. In medically justified cases, the investigator may use other medications (e.g., steroids as per local standard but not exceeding 10 mg prednisolone equivalent), doses and/or formulations if this is documented thoroughly in the eCRF and the source data. If no infusion reaction occurs during Cycle 1, then premedication can be stopped at discretion of the investigator for subsequent treatment cycles. Otherwise, the premedication should be continued for subsequent administrations of MOR03087 as well.

⁷ Emergency Laboratory only to be taken if hematology/serum chemistry is not available prior to study drug administration

⁸ Sample to be taken and evaluated before study drug administration. On Day 1, additional sample (except AST and ALT) to be taken 2 hours after end of infusion.

⁹ β2-microglobulin to be measured at Screening only.

¹⁰ Pharmacokinetic sample to be taken predose and then at 1, 2, 4, 8, 14±2 (optional), 22±2, and 28±2 hours after start of first infusion.

¹¹ Pharmacokinetic sample to be taken predose and 2 hours after start of infusion.

¹² Pharmacokinetic sample during treatment Cycles 3+ to be taken every 2nd study drug administration (CxD15) predose and 2 hours after start of infusion.

¹³ Only if subject had no follow-up visit.

¹⁴ Samples for anti-MOR03087 antibodies will also be used to determine tetanus titer if sufficient quantities of serum are available.

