## **11.1 Efficacy and Pharmacodynamic Assessments**

#### **11.1.1 Efficacy Assessment**

Efficacy will be evaluated in terms of overall response rate (ORR) (sCR + CR + VGPR + PR) (Kyle 2009), further tumor response rates (CR, sCR PR, MR, VGPR), SD rate, duration of response, TTP, and PFS, using the modified European Group for Blood and Marrow Transplantation (EBMT) criteria (Blade 1998) plus the International Myeloma Working Group Uniform Response Criteria (2006), taking the supplement by Kyle (Kyle 2009) into consideration.

All of these tumor response criteria for MM are defined in Appendix 18.3. All of them are based on the International Myeloma Working Group Uniform Response Criteria (Durie 2006 and

Erratum 2007), except for MR, which is based on the EBMT criteria (Blade 1998). Disease progression is defined as progressive disease according to the IMWG, 2006 (see Appendix 18.3, Table 14), death or start of new anti-MM treatment.

All responses need two consecutive assessments, ideally being confirmed at Day 1 of the next cycle.

The response evaluation will be based on serum and urine M-protein levels, serum FLC level, and FLC ratio.

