PD	
 
NOTE: Requires any one or more of the following: Increase of ≥ 25% from nadir in
 
Serum M-component and/or (absolute increase must be ≥ 0.5 g/dL)^g
 
Urine M-component and/or (absolute increase must be ≥ 200 mg/24 hours)
 
Only in patients without measurable serum and urine M-protein levels: the difference between involved and uninvolved FLC levels. Absolute increase must be > 10 mg/dL.
 
Bone marrow plasma cell percentage: absolute % must be ≥ 10%^h
 
Definite development of new bone lesions or soft tissue plasmacytomas or definite increase in the size of existing bone lesions or soft tissue plasmacytomas
 
Development of hypercalcemia (corrected serum calcium > 11.5 mg/dL or 2.65 mmol/L) that can be attributed solely to the plasma cell proliferative disorder
 

Table 14Response Criteria for Multiple Myeloma

Abbreviations: CR = complete response; FLC = free light chain; MR = minimal response; PD = progressive disease; PR = partial response; SD = stable disease; VGPR = very good partial response

- ^a All response categories require two consecutive assessments made at any time before the institution of any new therapy; all categories also require no known evidence of progressive or new bone lesions if radiographic studies were performed. Radiographic studies are not required to satisfy these response requirements.
- ^b Confirmation with repeat bone marrow biopsy not needed.
- ° Presence/absence of clonal cells is based upon the  $\kappa/\lambda$  ratio. An abnormal  $\kappa/\lambda$  ratio by immunohistochemistry and/or immunofluorescence requires a minimum of 100 plasma cells for analysis. An abnormal ratio reflecting presence of an abnormal clone is  $\kappa/\lambda$  of >4:1 or <1:2.
- ^d MR also includes subjects in whom some, but not all, the criteria for PR are fulfilled, provided the remaining criteria satisfy the requirements for MR.
- ^e The response criterion MR will not apply to subjects who present with serum FLCs only.
- ^f Per the International Myeloma Working Group Uniform Response Criteria (Durie 2006), stable disease is not recommended for use as an indicator of response; stability of disease is best described by providing the time to progression estimates.
- ^g For progressive disease, serum M-component increases of  $\geq 1$  g/dL are sufficient to define relapse if starting M-component is  $\geq 5$  g/dL.

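### Protocol Section 10.1.12 ties follow-up after visit 2 to an undefined response, unlike the rest of the plan, so subjects in stable disease could be censored early in PFS and TTP

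*Protocol*

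**What the plan says.** Protocol Section 10.1.12, under Follow-Up Visit 2 and Subsequent Follow-Up Visits, sets a condition: "If there is still a response to therapy at this visit, then a follow-up visit will be repeated every fourth week". The stopping events that follow are progression (with a 3-year limit), death and new anti-myeloma therapy. The list of procedures in the same section then states: "Response assessment, to be continued until disease progression or death or subsequent anti MM therapy start whatever occurs first".

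Protocol Section 7.1 covers subjects who stop drug for a reason other than progression. It says "all subjects will return for a follow-up visit 1 and follow-up visit 2", and then: "Further follow-up visits will be conducted at 4-week intervals until the subject is progressive, begins subsequent anti-myeloma therapy, or dies". Footnote 1 of Table 1 repeats the visit every fourth week "until progressive disease, or receipt of new anti-myeloma treatment, or until death, but no longer than 3 years from the first study drug administration", and footnote 1 of Table 2 is the same. SAP Section 3.1 repeats the rule of Section 7.1. None of these four places mentions response.

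The protocol uses the word response in two ways. In Section 11.1.1 the overall response rate counts PR or better, and a footnote to Table 14 in Appendix 18.3 says that "stable disease is not recommended for use as an indicator of response". For continuing treatment, however, Section 7.1 says "subjects who have an ongoing response of at least stable disease (SD) may continue treatment", and Section 10.1.13 uses the same broad sense.

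**The concern.** Section 10 is the visit-by-visit section that a site works from, and it holds the one rule that differs. The subjects at issue are those who stop study drug without progression. The protocol creates such cases: dose-limiting toxicity (Section 8.5), delays of more than 14 days (Section 8.6) and grade 3 or 4 infusion reactions (Section 9.1.3).

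If such a subject is in SD at follow-up visit 2 and the site decides that SD is not a response, the visits end there. PFS and TTP need assessments up to progression whatever the best response was. Ending them by response status makes the censoring depend on something that may be prognostic. The Kaplan-Meier estimate would then be too favourable if the subjects cut short are those likely to progress sooner.

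**Working it through.** The plan states no figure on this point, so there is nothing to reproduce. The check compares the texts, traces the censoring rules and adds an illustration of size.

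**1. The rules side by side**

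| Place | Condition on response | Visits or assessments run until |
|---|---|---|
| Protocol 10.1.12, opening sentence on visit 2 | Yes, undefined | progression (3-year limit), death, new therapy |
| Protocol 10.1.12, response-assessment item | None | progression, death, new therapy |
| Protocol 7.1 | None | progression, new therapy, death; 3 years from first dose |
| Protocol Tables 1 and 2, footnote 1 | None | same |
| SAP 3.1 | None | same |

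One sentence stands against all the others, including one in its own section.

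**2. What the condition does under each meaning**

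- At least SD: the condition means only that the disease has not progressed. Nobody is dropped.
- PR or better: subjects in SD stop at visit 2. Subjects in MR stop too, though a minimal response is a response by name.

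**3. Timing under the narrow meaning**

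Visit 1 is 4 weeks after the last dose and visit 2 is 4 weeks later: 4 + 4 = 8 weeks, or 56 days (each visit ±2 days). SAP Tables 2 and 3 censor a subject without progression at the last tumor assessment. They also censor an event found more than 65 days after that assessment (2 × 29 + 7 = 65). With the last assessment on day 56, a progression dated after day 56 + 65 = 121 from the last dose would be censored back to day 56, even if the site learned of it.

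**4. Illustration of size (every input is an assumption)**

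Half of the subjects are SD/MR and half are responders. PFS is exponential. A share f of the SD/MR subjects is censored at month 4 if still event-free, and everyone else is followed to month 36. There were 200,000 simulated subjects per row. Each arrow runs from full follow-up to follow-up cut at visit 2.

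| Median PFS, SD/MR vs responders (months) | f | Kaplan-Meier median | PFS at 6 months | Events unobserved |
|---|---|---|---|---|
| 6 vs 6 | 10% | 6.00 → 6.01 | 0.500 → 0.500 | 3.2% |
| 6 vs 6 | 25% | 6.01 → 6.01 | 0.501 → 0.500 | 7.7% |
| 6 vs 6 | 50% | 5.98 → 5.98 | 0.499 → 0.499 | 15.5% |
| 4 vs 12 | 10% | 6.64 → 6.71 | 0.531 → 0.534 | 2.7% |
| 4 vs 12 | 25% | 6.64 → 6.85 | 0.532 → 0.539 | 6.8% |
| 4 vs 12 | 50% | 6.64 → 7.17 | 0.531 → 0.548 | 13.3% |
| 3 vs 18 | 10% | 6.52 → 6.65 | 0.522 → 0.526 | 2.3% |
| 3 vs 18 | 25% | 6.52 → 6.86 | 0.522 → 0.533 | 5.6% |
| 3 vs 18 | 50% | 6.50 → 7.41 | 0.521 → 0.546 | 11.5% |

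The last column can be checked by hand. With medians m1 (SD/MR) and m2 (responders), the share of events unobserved is 0.5·f·(2^(−4/m1) − 2^(−36/m1)) / (1 − 0.5·2^(−36/m1) − 0.5·2^(−36/m2)). For 4 vs 12 and f = 0.5, this is 0.25 × (0.500 − 0.002) / (1 − 0.001 − 0.0625) = 0.1245 / 0.9365 = 0.133.

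With equal hazards the estimate loses events but does not shift. With SD/MR subjects progressing faster, the median rises by 0.07 months (6.71 − 6.64) to 0.91 months (7.41 − 6.50).

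**The case against.** The strongest reply is that the broad meaning is the natural one. Where the protocol uses response to decide who continues treatment, it includes SD, and Section 10.1.13 does so immediately after the sentence at issue. PR or better defines a rate for analysis, not a visit rule. The Table 14 footnote concerns how efficacy is reported, and the same table lists SD among its response categories. Section 7.1 says that visits follow the schedules, whose footnotes have no condition. Section 10.1.14 triggers the end-of-study visit by confirmed progression, withdrawal or 3 years, not by lack of response at visit 2.

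Much of this stands. It shows what was probably intended, and it rules out saying that subjects will be dropped. It does not remove the ambiguity. Where the protocol means at least SD it says so, and 10.1.12 lacks that qualifier. SAP Section 7.3.3.1 also codes MR and SD as no response, although sites do not work from the SAP.

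A reader might infer more than the documents support:

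- **That every subject stopping drug in SD or MR loses follow-up.** This holds only at a site that takes the narrow meaning and sets the schedule footnotes aside.
- **That these subjects leave the analysis.** They stay in the Kaplan-Meier estimate. What goes unobserved is their later course.
- **That duration of clinical benefit suffers for SD subjects.** It is calculated only after confirmed MR or better, so a subject whose best response is SD never enters it.
- **That Section 7.1 follows everyone to progression.** It also ends at new therapy, death or 3 years.

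**Conclusion.** The inconsistency is real: one conditional sentence conflicts with Section 7.1, both schedule footnotes, SAP Section 3.1 and an item in its own section. Its effect is possible, not established. It requires a site to read response as PR or better, and subjects who stop drug without progression while in SD (less plausibly MR) and have not started new therapy. For them, assessments could end about 8 weeks after the last dose, with censoring at the last tumor assessment in PFS and TTP, and in duration of clinical benefit only where MR or better was confirmed.

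Upward bias needs one further assumption, that these subjects have the worse prognosis. The documents give neither their number nor their prognosis, so the 0.1 to 0.9 month range is illustrative only. Event-free survival already counts treatment discontinuation as an event and is not affected.

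The affected endpoints are secondary and descriptive, and no dose decision or primary endpoint rests on them. The recommended-dose groups may, however, hold only 9 subjects (Protocol 15.9, SAP 5), so one subject is 1/9 = 11% of a group. It should be corrected, but it does not threaten the trial's main conclusions.

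**What to change.** In Protocol Section 10.1.12, replace the condition on response with this one: *If the disease has not progressed and no new anti-myeloma therapy has started*. Keep the 4-weekly interval and the 3-year limit as they stand. The section then agrees with Section 7.1, footnote 1 of Tables 1 and 2, SAP Section 3.1 and its own response-assessment item.

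The cost is one sentence. It adds no visits beyond those already required elsewhere in the protocol. The sponsor should also check whether any subject in SD or MR had visits stopped at follow-up visit 2, and identify such subjects in the PFS censoring listing that SAP Section 9.2 already plans.
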